Gamma Oscillation as a Potential Marker of rTMS Effects on the DLPFC. A better understanding of neural mechanisms holds the potential to yield clinically useful biomarkers predictive of rTMS treatment response. The availability of predictors would be useful because psychiatric treatments typically are ineffective for a substantial proportion of subjects and predictors would promote the judicious use of treatments so that only those individuals most likely to benefit are exposed to the risks and costs of treatment. The emerging literature on rTMS suggests that this treatment modality also suffer from this limitation. In the study by Barr et al., a substantial proportion of subjects did not benefit from TMS. In fact, a close examination of their data indicates that ~31.5% of subjects experienced lower performance post treatment compared to pre treatment. Although rTMS is generally considered safe, it, nonetheless, is a procedure that alters function of the targeted brain tissue. Thus, an additional goal of this proposal is to obtain preliminary support for pretreatment (baseline) gamma activity as a predictor of rTMS remediation of cognitive deficits in schizophrenia. We will evaluate the potential utility of gamma oscillations as a response predictor by testing whether baseline levels of gamma is associated post-treatment improvements in cognitive performance.

[figure not shown]
Innovation. The proposal represents an innovative approach to new treatment development for cognitive deficits associated with schizophrenia. We are not aware of any studies that have applied rTMS to Veterans for this purpose. The use of EEG frequency analysis to gauge the neurophysiologic effects of rTMS represents a novel combination of sophisticated methods. This combination also represents a mechanism-based approach to treatment development. Moreover, this approach promises to yield early indications for clinically relevant predictive information. We are not aware any studies that have examined potential predictors of rTMS efficacy to remediate cognitive deficits in schizophrenia. With the successful completion of this project, there is the potential translate our findings towards personalized treatment for Veterans suffering from cognitive deficits in schizophrenia.

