### Subjects

Table 1. Experimental Design

Clinical Assessment	Phase			
	Baseline	Randomization	Treatment	Post-treatment
	Week 1	End of Week 1	Wk 2 → Wk 6	Wk 7
Telephone Screen	WM Task		rTMS	WM Task

[figure not shown]

Figure 2. Scalp topography of control-related gamma oscillation power deficits in schizophrenia group compared to a healthy comparison group during the delay period of cognitive control task. Right frontal EEG leads show the most prominent deficits in schizophrenia. Left and right panels show superior and right lateral views respectively. From Minzenberg et al. [17].

Office Evaluations (SCID)	EEG Functional Status	[rTMS, Sham]	Sham	EEG Functional Status
---------------------------	-----------------------	--------------	------	-----------------------

A total of 24 subjects (12 rTMS and 12 sham) with SZ or SAD between the ages of 18 and 55 will be studied. Veterans will be recruited from a variety of sources including VAPHCS mental health clinics. We will consult with our system's Office of Data Analytics to identify potential subjects. We have already identified 366 veterans within the VAPAHCS population meeting the inclusion/exclusion criteria. We will work with this office to identify these veterans' VA clinicians who will assist in recruitment efforts. The study will be open to both men and women, regardless of race and ethnic origin. Details of demographics of the local VA population can be found in pg. 1 of the Human Subjects section.

Table 2. Inclusion and Exclusion Criteria

Exclusion Criteria	Inclusion Criteria
1) Pregnant or lactating female	1) Age 18-55 years
2) History of prior adverse reaction to TMS	2) SCID confirmed diagnosis of SZ or SAD
3) On medications known to significantly lower seizure threshold, e.g. clozapine, chlorpromazine, bupropion, clomipramine [21]	3) Stable medication regimen (no change in dose or agents within the 4 weeks prior to study entry and throughout the duration of the study)
4) History of seizures or conditions known to substantially increase risk for seizures	4) Stable social environment and housing to enable regular attendance at clinic visits
7) Implants or medical devices incompatible with TMS	5) Ability to undergo cognitive testing, EEG scans and rTMS
8) Acute or unstable chronic illness that would affect participation or compliance with study procedures, e.g. unstable angina	6) IQ > 80 (WASI full scale score)

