**Electroencephalography during Cognitive Task Performance:** All EEG gamma procedures have been employed in our published papers [16, 32, 33]. EEG data will be acquired in a shielded room using a Neuroscan 64-electrode Quik-Cap and Neuroscan SynAmps2 hardware, with 1000 Hz sampling rate and 100 Hz low-pass hardware filter, using 32-bit encoding software, eliminating the need for high-pass recording filters, and electrode impedances  $< 5$  k $\Omega$ . All channels will be referenced on-line to Cz. Malfunctioning electrodes are excluded and data imported into EEGLab, re-referenced against the average reference, downsampled to 250 Hz, and high-pass filtered at 0.5 Hz. Epochs are extracted from continuous EEG data on each task, from -500 to +3000 ms relative to stimulus onset, and baseline-corrected with pre-stimulus interval (-500 to 0 ms). Trials with incorrect responses are removed. Individual electrodes are excluded if voltage within that trial is  $> 5$  standard deviations from the mean of all electrodes. Independent Components Analysis (ICA) follows ([34] using the “logistic infomax” ICA algorithm [35] with “extended” option of [36]); 75 principal components accounting for the most variance in the signal are derived. Components among the top 15 are identified for rejection via visual inspection of equipotential scalp topography maps, component waveforms, and component time-frequency distributions, and comparison with the data in [37] and [38]. Time-frequency transformation of the data is performed [39] by convolving the epoched EEG with a complex Morlet wavelet function on individual trial segments to identify time-frequency components between 30-80 Hz. Each 1 Hz sub-band is defined by a logarithmically-increasing central frequency and range subject to a Gaussian kernel with constant  $c = 6$ . Average gamma power during the baseline is subtracted from task-related gamma power during the trial. Time-frequency

spectrograms are established by pooling oscillatory power across electrodes grouped by topography. Statistical thresholds are empirically-derived via a permutation method [40], to preserve frequency and time-specificity of task and treatment effects and to support statistical inferences made directly upon visual inspection of spectrograms [33, 41].

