## Statistical Analysis

**Hypothesis Testing, Aim 1 - Subjects receiving rTMS will show improvements in a) WM performance, and b) occupational/role functioning compared to subjects receiving sham treatment:** Change scores (post-TMS vs. pre-TMS) for WM performance accuracy ( $\Delta$ WM Acc) and Global Functioning ( $\Delta$ GF) will serve as dependent measures for testing the hypothesis that rTMS improves cognition and functioning, respectively. The hypothesis will be supported if we find greater  $\Delta$ WM or  $\Delta$ GF in the active compared to the sham rTMS treated groups. We will use independent samples t-tests and two-sided tests for significance testing, with an alpha level of 0.05. However, given the limited scope of the SPiRE award, our primary goal is not on finding statistically significant differences but rather on determining the directionality of changes and the effect sizes of treatment effects. These data will be critical for determining if there is preliminary evidence that could support proposals for future larger scale studies.

**Hypothesis Testing, Aim 2 - Subjects receiving active treatment compared to those receiving sham treatment will show a) increased cognition associated gamma oscillation power, and b) an associated improvement in task performance:** Hypothesis 2 will be supported if we find significantly greater  $\Delta$ gamma in the active rTMS compared to the sham treated group. In addition, in the active rTMS treated group, we will conduct Pearson's bivariate correlation between  $\Delta$ gamma and  $\Delta$ WM. A positive correlation between these variables will support the hypothesis that rTMS improves cognition by increasing gamma oscillations. We will explore the possibility that pre-treatment gamma predicts rTMS responsiveness. We will evaluate this possibility by conducting a median split analysis in which subjects will be binned by their baseline gamma levels. We predict that those in the lower half of the distribution will show higher  $\Delta$ gamma and  $\Delta$ WM.

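### The median split on pre-treatment gamma has no sham contrast, so regression to the mean favours the predicted change in gamma even if rTMS does nothing

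*Combined protocol and SAP*

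**What the plan says.** Under Aim 2 the Statistical Analysis section states: "We will explore the possibility that pre-treatment gamma predicts rTMS responsiveness". The method is "conducting a median split analysis in which subjects will be binned by their baseline gamma levels". The expected result follows: "We predict that those in the lower half of the distribution will show higher" change in gamma and change in WM.

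Nothing says whether the split uses the active arm or all subjects. No sham comparison, interaction term or test is named for it. The other two analyses in that paragraph do name their group. The main gamma test compares active with sham ("Hypothesis 2 will be supported if we find significantly greater" change in gamma in the active group), and the correlation is confined to one arm ("In addition, in the active rTMS treated group, we will conduct Pearson's bivariate correlation between" the two change scores).

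The Background section, in its paragraph on gamma as a potential marker, makes preliminary support for this predictor an additional goal. It describes the analysis as "testing whether baseline levels of gamma is associated post-treatment improvements in cognitive performance", again without mention of sham.

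**The concern.** The change in gamma is not defined separately, but Aim 1 defines its change scores as post against pre, and the natural reading is post minus pre. Pre-treatment gamma then appears twice: it assigns subjects to halves, and it enters the outcome with a minus sign. Subjects whose first reading was low partly by chance tend to rise at the second reading, and those who were high by chance tend to fall. The low half therefore gains more with no treatment effect, which is the pattern the plan would read as prediction of response.

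The change in WM does not contain pre-treatment gamma, so this bias is not automatic there. A separate problem applies to both outcomes. A low-versus-high difference without sham cannot separate prediction of rTMS response from change that would have differed by pre-treatment gamma anyway.

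Under Aim 1 the plan says that direction and effect size, more than significance, are what it wants to carry into larger studies. Those are the quantities that this artefact distorts.

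**Working it through.** The plan gives no effect size, power or error rate for this analysis, so there is no figure of its own to reproduce.

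**Inputs from the documents.** There are 24 subjects, 12 per arm (Subjects section). A split gives 6 v 6 if only the active arm is used and 12 v 12 if the arms are pooled. The two-sided t-test at 0.05 is stated under Aim 1 and assumed to carry over.

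**Assumptions.** rTMS has no effect. Pre and post gamma are bivariate normal with equal variance and correlation r. The documents do not give r, so I show a range. All 24 subjects have outcome data.

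**Expected gap.** In SD units, the mean change given pre-treatment value z is (r − 1)z. The mean of z is −√(2/π) = −0.798 in the low half and +0.798 in the high half. The large-sample gap in change, low minus high, is therefore

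(1 − r) × 2 × √(2/π) = 1.596 × (1 − r).

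This gives 0.80 SD at r = 0.5, 0.48 at 0.7, 0.32 at 0.8 and 0.16 at 0.9. It vanishes only as r approaches 1.

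**At the trial's sample size** (40,000 simulated null trials per setting, split at the sample median):

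| r | Subjects split | Gap (SD) | Predicted direction | p<0.05 in that direction |
|---|---|---|---|---|
| 0.5 | 12 (active) | 0.75 | 92% | 24% |
| 0.7 | 12 | 0.45 | 85% | 16% |
| 0.8 | 12 | 0.30 | 80% | 12% |
| 0.9 | 12 | 0.15 | 72% | 8% |
| 0.5 | 24 (pooled) | 0.77 | 98% | 50% |
| 0.7 | 24 | 0.46 | 94% | 31% |
| 0.8 | 24 | 0.31 | 89% | 22% |
| 0.9 | 24 | 0.15 | 81% | 13% |

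An unbiased analysis would give 0 SD, 50% and 2.5%.

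**Change in WM.** Here gamma and WM were each modelled as a stable trait plus session error, with an assumed trait correlation of 0.5, reliability of 0.5 to 0.8, and n=12. The session-error correlation is also assumed.

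| Session-error correlation | WM in predicted direction | Gamma and WM both in predicted direction |
|---|---|---|
| 0 | 50-51% | 41-47% |
| 0.3 | 60-65% | 52-62% |
| 0.5 | 66-74% | 59-71% |

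**With sham as the comparator, same null.**
- Same split within each arm, then the difference between arms: mean about 0 SD, predicted direction 50%, two-sided rejection 4.7-5.0%.
- Arm × continuous pre-treatment gamma interaction: predicted direction 50-51% and significant that way in 2.4-2.9%, across gamma and WM.

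**The case against.** The strongest reply is that this is one exploratory sentence in a 24-subject pilot. No treatment decision depends on it, and neither Aim 1 nor the active-versus-sham gamma test is touched. That is true, and it limits the severity. It does not remove the point, because the plan intends to use directions and effect sizes to support later work.

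Second, the Background section frames the predictor goal in terms of cognitive performance, so the gamma percentages do not bear on the goal as worded there. This is also right. But the Statistical Analysis section predicts the change in gamma as well, and for WM the absence of a sham contrast is enough to block a claim about response to rTMS.

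Third, the evidence for bias in WM is thin. The EEG section says "Trials with incorrect responses are removed", which might suggest that gamma and WM share session error. Under simple averaging, though, dropping trials makes gamma noisier without shifting its mean, and simulating that mechanism alone left the WM direction at about 50%. Shared error could arise in other ways, such as alertness, but the documents do not quantify it. The WM figures above 50% are illustrations only.

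Fourth, the plan is silent on sham here and does not rule it out. But both natural readings of the text, active arm only or both arms pooled, give the biased result, so this is more than a missing detail.

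Finally, keeping the split and adding a between-arm contrast would also remove the bias. That is correct, and it is the minimum change. The continuous interaction is preferred because it does not discard information by dichotomising 12 subjects per arm.

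**Conclusion.** The concern holds. As written, the gamma half of the predictor analysis is likely to come out as predicted when rTMS does nothing: in 80-92% of trials with the active arm alone and 89-98% with both arms pooled, for r between 0.5 and 0.8. At r = 0.9 the figures are still 72% and 81%. The spurious gap is about 0.3 to 0.8 SD of pre-treatment gamma for r of 0.5 to 0.8, and 0.15 SD at 0.9. These sizes rest on assumed values of r and on equal pre and post variance. The direction of the bias, given equal variance, needs only r below 1. The rejection rates (12-24% and 22-50% for r of 0.5 to 0.8) also assume that the Aim 1 t-test is used.

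For WM there is no automatic bias. The fault is that the analysis lacks the comparison needed to speak of response to rTMS. This should be corrected before the analysis is run. It does not threaten the main comparisons.

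**What to change.** Replace the median-split wording under Aim 2 as follows.

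- Include all analysed subjects from both arms and keep pre-treatment gamma continuous.
- Gamma: regress post-treatment gamma on arm, pre-treatment gamma and arm × pre-treatment gamma.
- WM: regress post-treatment accuracy on arm, pre-treatment accuracy, pre-treatment gamma and arm × pre-treatment gamma.
- Base any statement about pre-treatment gamma as a predictor of response on the interaction. Report it as an estimate with a 95% CI, labelled exploratory, with no pass/fail rule.
- Keep the median split, if wanted, only as a descriptive display shown separately by arm.

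The cost is wording only, since the data are already planned. The drawback is precision. With 12 per arm and r from 0.8 down to 0.5, the median 95% CI half-width for the gamma interaction is about 0.56 to 0.81 SD per SD of pre-treatment gamma (0.57 to 0.82 for WM). Power in the predicted direction is 23-42% for a true slope difference of 0.5 and 11-18% for 0.3. The result will look less favourable than the split would, which is why an estimate with its interval is asked for and not a test.

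### The exploratory baseline-gamma predictor question is analysed only by a median split; if gamma is roughly normal and the relation linear, this keeps about 64% of the information and shrinks the correlation by about 20%

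*Combined protocol and SAP*

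**What the plan says.** Background and Significance (paragraph on gamma as a potential marker of rTMS effects) states that "an additional goal of this proposal is to obtain preliminary support for pretreatment (baseline) gamma activity as a predictor" of cognitive benefit. It says this will be done by "testing whether baseline levels of gamma is associated post-treatment improvements in cognitive performance". That is a question about level, on a continuous scale.

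The EEG paragraph of Research Design and Methods confirms the scale: "Average gamma power during the baseline is subtracted from task-related gamma power during the trial".

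The Aim 2 paragraph of Statistical Analysis introduces the analysis as exploratory: "We will explore the possibility that pre-treatment gamma predicts rTMS responsiveness". The method is "conducting a median split analysis in which subjects will be binned by their baseline gamma levels", and the expected result is "We predict that those in the lower half of the distribution will show higher" changes in gamma and in working memory (WM). It names no test, no restriction to one arm and no comparison with sham for this analysis. The same paragraph does use a continuous method, Pearson's correlation in the active arm, to relate change in gamma to change in WM.

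The sample size is "A total of 24 subjects (12 rTMS and 12 sham"). Under the modified intent-to-treat rule only subjects with outcome data are analysed, so 24 is an upper limit.

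**The concern.** A median split treats two subjects just either side of the sample median as opposites, and treats a subject at the extreme like one near the middle. The documents give no biological or clinical reason for a cut at that point. They also give no reason for handling baseline gamma differently from change in gamma, which the same paragraph keeps continuous.

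At stake is the yield of a named additional goal of the proposal. The trial is meant to inform larger studies, and for that a slope with a confidence interval is more useful than a difference between two halves defined by this sample. If the relation is graded, the split weakens both the test and the effect size that would be carried forward.

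**Working it through.** The documents give no power figure, expected correlation or gamma distribution for this analysis, so there is no figure of the plan's own to reproduce.

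**Inputs.** From the documents: 24 subjects, 12 per arm, and a continuous predictor cut at its median. Assumed: a standard normal predictor, a linear relation with correlation r, and two-sided α = 0.05. The plan specifies "independent samples t-tests and two-sided tests for significance testing, with an alpha level of 0.05" under Aim 1; extending that to the predictor analysis is an assumption.

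**Step 1, information kept.** For a standard normal x, the correlation between x and its upper/lower-half indicator is E|x| = √(2/π) = 0.798.
- The observed correlation is multiplied by about 0.80, a shrinkage of about 20%. A true 0.5 becomes about 0.40.
- The information kept is 0.798² = 2/π = 0.637, so 36% is lost. By simulation at these sample sizes the loss is 36.2% at n = 24 and 35.7% at n = 12.
- In equivalent subjects: 24 × 0.637 = 15.3, and 12 × 0.637 = 7.6.

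**Step 2, power.** Each simulated data set was tested with t = r̂ √[(n − 2)/(1 − r̂²)] on n − 2 degrees of freedom, first with x continuous and then with the half indicator (200,000 replicates per cell).

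| Assumed r | All 24: continuous v split | Active 12: continuous v split |
|---|---|---|
| 0.3 | 30% v 20% | 16% v 11% |
| 0.5 | 73% v 50% | 40% v 24% |
| 0.6 | 90% v 70% | 58% v 35% |

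Separate runs of the 24-subject split cell at r = 0.5 gave 50% to 51%.

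**Step 3, the contrast that addresses response to rTMS.** The model is change = b0 + b1·arm + b2·gamma + b3·arm × gamma, with 12 per arm, correlation r in the active arm and none in sham. Power for b3, continuous v split at the pooled median:
- r = 0.3: about 10% v 8%
- r = 0.5: about 21% v 15%
- r = 0.7: about 40% v 27%

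**Step 4, departures from the assumptions (n = 24, r = 0.5).**
- Log-normal gamma left untransformed, with r on the log scale: 58% v 50%. The continuous analysis still leads, but by less; taking logs restores 73% v 50%.
- A true step at the median, with r the correlation between outcome and true half: 52% v 59%. Here the split does better.

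**Step 5, regression to the mean.** Change in gamma contains baseline gamma. With no treatment effect and equal variances, the correlation of baseline with change is −√[(1 − ρ)/2] for test-retest correlation ρ. For assumed ρ of 0.5, 0.7 and 0.9 this gives −0.50, −0.39 and −0.22. The predicted direction can therefore appear within an arm without any treatment effect, whether gamma is split or continuous. Only the comparison of slopes between arms separates the two.

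**The case against.** The strongest case against acting has four parts.

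**The analysis is exploratory.** The plan says so, seeks only preliminary support, and states under Aim 1 that direction and effect size matter more than significance. This stands, and it limits the weight of the power figures. It does not remove the point, because the split also shrinks the effect size.

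**The size of the loss rests on assumptions.** A reader might infer that the split simply discards a third of the information from 24 subjects. The documents do not support that as a fact. They give no distribution for gamma and no shape for the relation, and they do not say whether the split uses all subjects or only the active arm. The prediction is worded as lower half against upper half, so a step-like effect is not excluded, and under a true step at the median the split is the better analysis. Nothing in the documents argues for such a step, however.

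**The trial would probably miss the predictor either way.** For the arm-by-gamma term this is largely right: about 10% v 8% at r = 0.3 and 21% v 15% at r = 0.5. The large gap at r = 0.5 with all 24 subjects comes from pooling the arms, which tests a general association with baseline gamma and not response to rTMS.

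**A sample-specific cut does little harm in a pilot.** The plan proposes no clinical cut-off, so this is fair. The remaining cost is the attenuated estimate and the lack of a slope.

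**Conclusion.** The point holds as a worthwhile, low-cost improvement to one exploratory analysis. With gamma roughly normal on the analysis scale and a linear relation, the median split keeps about 64% of the information and shrinks the correlation by about 20%, whichever set of subjects is used. The loss is smaller with skewed, untransformed gamma and reverses with a true step at the median.

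Two stronger readings are not supported. The split does not affect the treatment comparisons of WM, functioning or gamma under Aims 1 and 2. Removing it would not make the trial well powered to find a predictor of rTMS response, since power for the slope difference is only about 40% even at r = 0.7 in the active arm and none in sham. The benefit is mainly a less attenuated, more precise estimate for planning a later trial.

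**What to change.** In the Aim 2 paragraph, replace the median split as the main predictor analysis with a linear model of change in WM, and a second one of change in gamma. Each should have terms for arm, baseline gamma as a continuous variable, and their product.

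- Look at the distribution of baseline gamma before fitting, and log-transform or otherwise rescale it if it is skewed.
- Report the slope in each arm and the slope difference with 95% confidence intervals, and a scatter plot by arm. For change in gamma, rest the interpretation on the slope difference because of regression to the mean.
- Keep the low/high grouping for display only.
- State that the analysis is exploratory and that power for the product term is low even with continuous gamma.

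The cost is a few sentences of analysis text; data and visits are unchanged. The downside is the assumption of an approximately linear relation, which the scatter plot lets readers check.

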**Intent-to-treat:** We will conduct a modified ITT analysis for hypothesis testing. We will use a modified ITT, which includes only subjects with outcome data, e.g. cognitive performance and EEG at the end of treatment [43], since good proxy measures cannot be imputed. To minimize missing data, we will acquire cognitive performance and EEG within one week of their last TMS session, including those intending to drop out. We will supplement this analysis with a per protocol analysis in which only subjects who completed all TMS treatments will be compared. This is done to determine, in a proof of concept manner, if TMS has the capacity to improve cognition in schizophrenia. We will include a careful examination of whether bias has been introduced due to dropout by determining if there is greater dropout in the treatment group and if significant differences exist in

major demographic and clinical variables of individuals who have dropped out compared to those who have not. We will correct for any significant differences using covariates in our statistical models.

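### The modified ITT set is an outcome-observed set analysed by change-score t-test: baseline-related dropout can bias it, and no analysis shows how far the effect size depends on missing outcomes

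*Combined protocol and SAP*

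**What the plan says.** The Intent-to-treat paragraph of Statistical Analysis defines the set for hypothesis testing: "We will use a modified ITT, which includes only subjects with outcome data". The reason given is "since good proxy measures cannot be imputed". Three further provisions stand in the same paragraph.

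- **Early capture of outcomes:** "we will acquire cognitive performance and EEG within one week of their last TMS session, including those intending to drop out".
- **A supplementary set**, offered as proof of concept: a "per protocol analysis in which only subjects who completed all TMS treatments will be compared".
- **A dropout check:** "We will include a careful examination of whether bias has been introduced due to dropout". It compares dropout between arms, and compares dropouts with the rest on major demographic and clinical variables. Then: "We will correct for any significant differences using covariates in our statistical models".

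The Aim 1 paragraph tests change scores in working-memory (WM) accuracy and Global Functioning (GF) with two-sided independent-samples t-tests at 0.05. It says that the primary goal is direction and effect size, not significance. The Subjects section gives the sample: "A total of 24 subjects (12 rTMS and 12 sham) with SZ or SAD". Table 1 shows one baseline and one post-treatment assessment.

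**The concern.** Both analysis sets select on something that happens after randomisation: having an outcome, or finishing every session. Treatment is 20 daily sessions of about 50 minutes, so attendance could plausibly depend on how impaired a subject is at the start or on how treatment is going.

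These are two different problems. Dropout related to baseline biases a change-score comparison through regression to the mean, and the observed data can correct that. Dropout related to the unseen outcome cannot be corrected from the observed data; one can only show how much it would matter. The plan handles the first only through a significance-triggered adjustment and does nothing about the second. What is at stake is the effect size, which the plan names as its main product and intends to carry into larger trials.

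**Working it through.** The documents give no power, SD or dropout rate, so there is no stated figure to reproduce. Inputs from the documents are 12 per arm, one baseline and one post-treatment assessment, and the change-score t-test. The d = 0.92 below is the cited trial's effect in the Background, used only as a scale. Dropout numbers, shifts and correlations are assumptions.

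**1. Who is in each set.**

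| Subject | Modified ITT | Per protocol |
|---|---|---|
| All sessions, assessed | in | in |
| Stopped early, assessed | in | out |
| Not assessed | out | out |

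The per protocol comparison therefore adds no information about unassessed subjects.

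**2. What the dropout check can detect.** Fisher's exact test, 12 v 12:

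- 4 v 0 dropouts: p = 0.093
- 5 v 0: p = 0.037, the first count against zero that is significant
- 6 v 1: p = 0.069

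Its power is 9.5% for true dropout of 30% v 10%, and 23% for 40% v 10%. For the check on characteristics, a t-test of 4 dropouts against 20 others has 29% power for a 0.8 SD difference. Any resulting correction is made among subjects with outcomes, and baseline WM is not named as a covariate.

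**3. Dropout related to baseline.** Take equal SDs at the two times, correlation r, and no treatment effect. The expected change given a baseline of z SDs is (r − 1)z. Suppose the 3 lowest-baseline active subjects of 12 are lost and sham is complete. The expected normal order statistics of the three lowest are −1.629, −1.116 and −0.793, which sum to −3.538. The other nine then have mean baseline 3.538/9 = 0.393 SD. The bias of the change-score difference is (r − 1) × 0.393:

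- r = 0.7: −0.3 × 0.393 = −0.118 SD
- r = 0.3: −0.7 × 0.393 = −0.275 SD

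These are SDs of a single score. The bias is against active treatment here; losing the highest-baseline active subjects would reverse the sign. A simulation of this scenario gave −0.115 and −0.277 for the change score, and −0.001 to 0.001 for the baseline-adjusted estimate. The standard error was 0.34 (change) v 0.33 (adjusted) at r = 0.7, and 0.51 v 0.44 at r = 0.3.

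The residual variance is 2(1 − r) for change scores and 1 − r² after adjustment. The ratio is (1 + r)/2, which is 0.85 at r = 0.7 and 0.65 at r = 0.3. Adjustment costs one degree of freedom.

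**4. What a joint model adds.** With a common baseline mean, the likelihood is f(baseline) × f(post given baseline, arm). A subject with baseline only contributes to the first factor, which holds no arm effect. The estimate is therefore that of ANCOVA on outcome-observed subjects. Four simulated 12 v 12 data sets, with 3 active and 1 sham outcome missing, agreed to at least six decimals.

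**5. Dropout related to the unseen outcome.** Let m of 12 active subjects be missing, with mean change lower by s (in SDs of change) than that of observed active subjects, and let sham be complete. Holding the SD fixed, d over all randomised = observed d − (m/12)s.

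- m = 3, s = 1: the difference moves by 3/12 × 1 = 0.25 SD
- m = 2, s = 0.5: 2/12 × 0.5 = 0.08 SD
- Observed d = 0.92, s from 0.5 to 2.0: 0.84 to 0.59 for m = 2; 0.80 to 0.42 for m = 3
- Missing subjects did better, m = 3, s = −1: 0.92 + 0.25 = 1.17

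The estimate reaches zero at s = 12d/m. For d = 0.92 and m = 3 that is 3.68 SD; for an assumed d = 0.25 and m = 3 it is 1.0 SD. Missing sham outcomes enter with the opposite sign.

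**The case against.** The plan is better protected than its analysis sets alone suggest. A reader might infer that the modified ITT is restricted to treatment completers. The documents do not support that: early stoppers who are assessed stay in, and early capture is aimed at exactly this missingness. A reader might also infer that the per protocol analysis is the only back-up, or is meant as a bias check. Neither holds: it is described as proof of concept, and a separate dropout check with covariate correction is planned.

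It is also tempting to say that a likelihood model would keep every randomised subject. It would do so only in name (step 4). With a single post-treatment assessment there is no intermediate outcome to borrow from, so the plan's remark about imputation has some force. Nor do the documents support saying that the effect will be overstated by 0.25 SD: the numbers lost and the shift are chosen, and the sign can go either way.

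Finally, this is an openly described 24-subject pilot, and Preliminary Studies reports no dropouts among 27 subjects in an earlier rTMS study. That is reassuring, although that study's primary goals differed and its number of sessions is not given.

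What stands of the criticism: the dropout check has little power at this size and cannot reach outcome-dependent dropout, the main test ignores baseline unless a significant difference triggers adjustment, and nothing varies the assumption about missing outcomes. Early capture also names cognition and EEG but not GF, which is an Aim 1 outcome.

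**Conclusion.** The concern holds in a limited form. The set is outcome-observed, and the analysis on it is open to bias from baseline-related dropout: about 0.12 to 0.28 SD if three of 12 active subjects are lost at the low end of baseline and the correlation is 0.7 to 0.3. Baseline adjustment removes that bias when the baseline relation is linear and dropout depends on baseline alone. It leaves untouched any bias from outcome-dependent dropout, such as the 0.25 SD illustration, whose effect on the reported estimate the plan gives no way to judge. Both sizes rest on assumed losses; with complete outcomes both vanish. Because the effect size is the pilot's stated product, the change is worth making, but it does not call the design into question.

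**What to change.** 1. Call the set *outcome-observed*, and state for each outcome (WM, GF, gamma) what a subject needs in order to be included. Extend the early-capture commitment to GF.
2. Replace the change-score t-test for WM and GF with a pre-specified comparison of post-treatment scores adjusted for baseline (ANCOVA, or the equivalent two-time-point model with a common baseline mean). Say plainly that this does not recover unobserved subjects, and reconcile it with the significance-triggered covariate rule.
3. Report all 24 randomised subjects by arm, with outcome status and reasons for missing outcomes.
4. Add a delta-adjusted table over all 24. Predict each missing outcome from baseline, then shift it, in either arm and in both directions. Give the shift at which the estimate reaches zero. This assumes a baseline for everyone randomised, as Table 1 implies by placing randomisation at the end of the baseline week.

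The cost is a SAP paragraph and a little more analysis. The only addition to data collection is the GF rating in subjects who stop early.
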